5.3.6 Other Considerations

Not Applicable.

5.4 EFFICACY ANALYSES

5.4.1 Primary Efficacy Analyses

The primary analysis will be based on subjects from the Full Analysis Set with the prespecified censoring rules applied. The primary endpoint is the change from baseline to 12 months in the derived ADCOMS. The derived ADCOMS is a weighted linear combination of 12 items from the three existing clinical scales, the ADAS-cog, the MMSE, and the CDR. These 12 items consist of the predictive variables A4, A7, A8, A11, M1, M7, C1, C2, C3, C4, C5 and C6, which have been selected from the clinical scales, the ADAS-cog, the MMSE, and the CDR. The names of these item and the corresponding scale names are described in [Table 2](#).

Table 2: Predictive Variables for the Derived ADCOMS

Scale	Item ID	Item Name	PLS weight
ADAS-cog	A4	Delayed Word Recall	0.00847483
	A7	Orientation	0.017088
	A8	Word Recognition	0.003732761
	A11	Word Finding	0.016211
MMSE	M1	Orientation Time	0.041567
	M7	Drawing	0.038238
CDR	C1	Personal Care	0.054321
	C2	Community Affairs	0.1091
	C3	Home and Hobbies	0.089039
	C4	Judgment and Problem Solving	0.069493
	C5	Memory	0.058724
	C6	Orientation	0.078152

ADAS-cog = Alzheimer's Disease Assessment Scale, cognitive subscale, CDR = Clinical Dementia Rating, ID = identification, MMSE = Mini Mental State Examination, PLS = Partial Least Squares.

The derived composite score will be calculated from these predictive variables according to the formula:

$$\text{Derived composite Score} = A4 * 0.00847483 + A7 * 0.017088 + A8 * 0.003732761 + A11 * 0.016211 + (5-M1) * 0.041567 + (1-M7) * 0.038238 + C1 * 0.054321 + C2 * 0.1091 + C3 * 0.089039 + C4 * 0.069493 + C5 * 0.058724 + C6 * 0.078152.$$

The maximum derived composite score is achieved when each item is assigned the maximum score. This maximum composite score is 1.97. The range of this new composite score is therefore between 0 and 1.97.

The primary endpoint is the change from baseline to 12 months in the derived ADCOMS. The primary efficacy analysis is based on Bayesian statistics. The dose-response of the primary endpoint is modeled with a two-dimensional first-order normal dynamic linear model (NDLM), where Normal and Inverse-Gamma priors are used. The primary efficacy analysis will calculate the Bayesian posterior probability that the dose identified is the most likely ED₉₀ dose that achieves the CSD compared to the placebo arm. At each analysis, three Bayesian probabilities will be summarized for each active dose: the probability of being the ED₉₀ dose, the probability of being statistically superior to placebo, and the probability of being statistically superior to placebo by the CSD. The study will be considered a success in the Bayesian analysis at the completion of 12 months of treatment if there is at least an 80% probability that the ED₉₀ achieves the clinically significant difference from placebo. See [Section 5.4.2](#) for definitions of CSD, ED₉₀, early success and futility.

Censoring

For the clinical efficacy data (i.e. derived ADCOMS, MMSE, CDR-SB, ADAS-cog and FAQ)

- Subjects will be censored at the time of initiation of new AChEIs or memantine treatment regimens if they were not on AChEIs or memantine at randomization, and will be censored at the time of dose adjustment of AChEIs or memantine if they were already on stable treatment with AChEIs or memantine at randomization.

The value of the primary endpoint for censored subjects and censored assessments will be imputed using data up to the censoring time and the Bayesian imputation method.

5.4.1.1 Sensitivity Analyses

After unblinding, the primary endpoint will be analyzed using the Bayesian methods described above. The following additional Bayesian analyses will be conducted using the Full Analysis Set:

- The primary endpoint will be analyzed regardless of initiation of new AChEIs or memantine or dose adjustment of stable AChEIs or memantine, using the same Bayesian analysis method as in the primary analysis. This is an intent-to-treat analysis without any censoring.
- In case of early success, the primary analysis as well as the above sensitivity analysis will be repeated after all subjects have either completed 12 months follow-up or are lost to follow-up.

5.4.1.2 Conventional Analyses

Statistical methods for the conventional analyses of primary efficacy endpoint will use a mixed effects model with repeated measures (MMRM) comparing placebo to the identified ED₉₀ dose from the Bayesian analysis. The model will include baseline ADCOMS as covariate, with treatment group, visit, randomization stratification variables (i.e., clinical subgroup [MCI due to AD, Mild Alzheimer's Disease Dementia], the presence or absence of ongoing AD treatment [AChEIs or memantine or both], *APOE4* status [positive, negative]), region, treatment group-by-visit interaction as fixed effects. If there is an imbalance across treatment groups based on randomization stratification variables, additional MMRM model will be run without the randomization stratification variables. In addition, ANCOVA model will also be used with treatment as a factor and baseline value as a covariate.

An unstructured covariance matrix will be employed in the MMRM to model the covariance of within subject effect. These analyses will be performed using all randomized subjects in the full analysis set as well as in the per protocol set. There will be no conventional analysis at each interim analysis before early success is claimed and as such there will be no multiplicity adjustment made to account for the interim analyses. In case of early success, the conventional analyses will be performed using the data collected prior to the interim analysis as well as at the end of 12 months assessment, and the analysis at the end of 12 months assessment will be considered as sensitivity analysis to the analysis at early success.

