5.4.4 Secondary Efficacy Analyses

The Full Analysis Set will be used in secondary efficacy analyses.

Key Secondary Endpoint Analyses

Key Secondary endpoints and corresponding analyses are ordered to reflect the most recent FDA draft guidance (February, 2018) and EMA Final Guideline (February, 2018) that prioritize effects on pathophysiology in early AD, as measured by biomarkers. Conventional analysis will be performed using all available data at the time of success (if applicable), and at 18 months of treatment, regardless of success. As described in section 5.4.1.2, conventional analysis will be based on the MMRM model including baseline as covariate, with treatment group, visit, randomization stratification variables (i.e., clinical subgroup [MCI due to AD, Mild Alzheimer's Disease Dementia], the presence or absence of ongoing AD treatment [AChEIs or memantine or both], *APOE4* status [positive, negative]), region, treatment group-by-visit interaction as fixed effects. If there is an imbalance across treatment groups based on randomization stratification variables, additional MMRM model will be run without the randomization stratification variables. In addition, ANCOVA model will also be used with treatment as a factor and baseline value as a covariate. These statistical models will be used to compare the combined 10 mg dose group (including bi-weekly and monthly regimens) with placebo for the key secondary endpoints. The rationale for combining the two 10 mg dose regimens is to account for the loss of subjects positive for *APOE4* in the 10 mg/kg biweekly dose group and the inability to randomize *APOE4* carriers to the 10 mg/kg biweekly group following a regulatory request by European Health Authorities in July 2014.

In addition, analysis will be performed for the following treatment comparisons:

- Combining 2 high doses (10 mg bi-weekly + 10 mg monthly), 2 middle doses (5 mg bi-weekly + 5 mg monthly), and the 2.5 mg bi-weekly dose, resulting in 3 treatment comparisons with placebo (for dose response)
- ED₉₀ dose of BAN2401 versus placebo, where the ED₉₀ dose of BAN2401 will be established by Bayesian analysis at 18 months as described in the next paragraph
- By treatment regimen (10 mg bi-weekly, 10 mg monthly, 5 mg bi-weekly, 5 mg monthly, 2.5 mg bi-weekly, placebo)
- Combining the top 3 doses (10 mg bi-weekly, 10 mg monthly, and 5 mg bi-weekly) versus placebo

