8.1 DEFINITION OF VISIT WINDOWS

The protocol specified visits/weeks and corresponding time windows used for visit-wise analyses are presented in terms of days relative to the first dose. For subjects that are randomized, the last available assessment on or before the date of the first dose of study drug will be used as the Baseline-Day 1.

Different assessment may have different visit schedule. A general rule for determining a time window for each scheduled visit is to split the two consecutive scheduled visits in the middle point of the two consecutive visits. For example, the time window for visit X is from the middle

point between visit (X-1) and X (exclusive) to the middle point between visit X and (X+1) (inclusive). According to protocol, “assessments should take place on the first day of the study visit in the designated study week except as noted below (footnotes h, i, and j pertaining to imaging assessments, and footnote o pertaining to CSF sample collection)” (see [page 96, Protocol Amendment 08](#)). Therefore, the scheduled day corresponding to scheduled visit at week Y is $((Y-1)*7+1)$ days. For example, the scheduled day for scheduled visit at weeks 1, 3, and 5 are Day 1, Day 15, and Day 29, respectively and the corresponding time window for scheduled visit at weeks 1 and 3 are [Day 1, Day 8] and [Day 9, Day 22], respectively

For scheduled every 3 months post baseline efficacy assessments, the analysis visits are the same as the scheduled visits. Any window rules will not apply. This is per ITT principle and also assumes that the actual assessment dates are independent from any other factors or are random and centered at scheduled time point.

For Early Termination (ET) visit and Follow Up (FU) visit, the following rules apply for efficacy assessment:

- If the last scheduled 3-month assessment before early termination (LS), ET assessment and FU assessment are in three separate sequential 3-month windows, e.g., Window(x), Window (x+1) and Window(x+2), then the analysis visits for last scheduled 3-month assessment (LS), ET assessment and FU assessment will be x, x+1 and x+2, respectively.
- If both LS and ET are in Window(x) and FU is in Window(x+1) [note: this is the most likely situation since ET and FU are expected to be separated by 3 months], then analysis visit is x for LS (per rule 1.) and (x+1) for FU and ET will not be included in Bayesian analyses and MMRM analyses.

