2.2 Dose-Response Model Primary

We label the mean change from baseline to 52-weeks for dose group d as θ_d . We construct a dose-response model for the mean change from baseline for each treatment arm. The arms are modeled with a two-dimensional first-order normal dynamic linear model (NDLM). This model is a Gaussian random walk model. The structure is

$$\begin{aligned} [\theta_0] &\sim N(0, 0.5^2) \\ [\theta_1] &\sim N(0, 0.5^2) \end{aligned}$$

□

and the NDLM structure for the bi-monthly doses:

$$[\theta_2] \sim N(\theta_1, \tau^2)$$

□

$$[\theta_3] \sim N(\theta_2, \tau^2)$$

The monthly doses are “connected” to the dose-response model through the respective bi-monthly doses. The connection through the NDLM first order structure results in the following priors

$$[\theta_4] \sim N(\theta_2, \tau^2)$$

and

$$[\theta_5] \sim N\left(\frac{\theta_3 + \theta_4}{2}, \frac{\tau^2}{2}\right).$$

The drift parameter (variance component), τ^2 is modeled with the following prior distributions:

$$[\tau^2] \sim IG(0.25, 0.0025)$$

where $IG(a, b)$ is the inverse gamma distribution with shape parameter a and scale parameter b . This prior has the equivalent weight of 0.5 observations worth of weight that the value of τ is 0.1.

The prior distribution on the initial dose is selected to be a vague prior. An effect size of 0.03 is considered clinically significant and the standard error of the clinical scale is 0.15. Therefore these priors are quite weak and allow the data to shape the dose-response model. The prior for the “drift parameter” is selected to have minor weight that there will be similarity across the doses, and hence a minor amount of borrowing. With 5 doses the amount of borrowing is determined largely by the similarity in outcomes across doses.

The distribution of the variance of the primary endpoint, σ^2 , is modeled with the following prior:

$$[\sigma^2] \sim IG(2.5, 0.056).$$

The prior is equivalent to a prior weight of 5 observations worth of information that the value of σ is 0.15. The value of 0.15 is based on initial modeling by Eisai. This prior allows the historical data estimate of 0.15 to have some role in the early part of the trial. When 300 subjects have been enrolled this prior will have a very minor role (5/305 weight is less than 2%).

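### The MMRM has no baseline-by-visit term, so one baseline slope serves all visits and the 18-month adjustment of the clinical scales may be weakened

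*SAP*

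**What the plan says.** Section 5.4.1.2 defines the conventional model for ADCOMS: "The model will include baseline ADCOMS as covariate, with treatment group, visit, randomization stratification variables", and then "region, treatment group-by-visit interaction as fixed effects". Baseline is a main effect. Treatment by visit is the only term that lets an effect differ between visits. On the residuals the section says "An unstructured covariance matrix will be employed in the MMRM".

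Section 5.4.4 carries this to the key secondary endpoints at 18 months: "conventional analysis will be based on the MMRM model including baseline as covariate, with treatment group, visit, randomization stratification variables". The list of terms is otherwise the same. Section 5.8 refers back to the same MMRM for the remaining clinical time points and repeats its structure in the models that relate baseline biomarkers to clinical change. None of the three sections lists a baseline-by-visit term.

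Sections 5.4.1.2 and 5.4.4 also plan a second model: "ANCOVA model will also be used with treatment as a factor and baseline value as a covariate". On visits, Section 8.1 states: "For scheduled every 3 months post baseline efficacy assessments, the analysis visits are the same as the scheduled visits".

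**The concern.** A common slope says that a given difference in baseline score predicts the same difference in change at month 3 as at month 18. In a progressive disease this is doubtful: change accumulates, and its dependence on baseline may accumulate with it.

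With an unstructured covariance, the common slope is a weighted average of the visit-specific slopes, and the weights favour visits with small residual variance. If the spread of change grows over time, those are the early visits, where baseline predicts least. The fitted slope is then too shallow at 18 months, the visit at which the key secondary clinical comparisons are made. Part of the variance that baseline could explain stays in the residual, and a chance baseline difference between arms is only partly corrected.

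**Working it through.** The SAP gives no power, standard error or sample size for the MMRM, so there is no planned figure to reproduce.

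**Inputs from the SAP**
- Model terms and unstructured covariance: Section 5.4.1.2.
- Efficacy visits every 3 months (Section 8.1), taken as months 3, 6, 9, 12, 15 and 18.
- Visit-to-visit correlation 0.80: simulation plan, Section 8.1.
- One-sided 5% level: Section 5.
- ADCOMS spread at 12 months only: "the standard error of the clinical scale is 0.15" (simulation plan, Section 2.2), read as an SD.

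**Assumptions, not in the SAP**
- True baseline slope proportional to time.
- Correlation of baseline with 18-month change ρ = 0.3 (0.2 and 0.4 as a range).
- Correlation falling as 0.8 per visit step, AR(1).
- SD of change constant, or growing as time to the power 0.25, 0.5 or 1.

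**Formulas.** Let S be the residual covariance across visits and β the vector of true visit-specific slopes. The common slope converges to

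b = (1′S⁻¹β) / (1′S⁻¹1).

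Scale baseline and 18-month change to SD 1. Then β₁₈ = ρ, and the 18-month residual variance with the correct slope is 1 − ρ². With r = b/β₁₈:
- variance ratio (common slope against visit-specific slopes) = 1 + ρ²(1 − r)² / (1 − ρ²);
- share of the baseline adjustment retained = 1 − (1 − r)²;
- power, for a comparison with 80% under visit-specific slopes = Φ(2.486/√ratio − 1.645).

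At ρ = 0.3 the multiplier ρ²/(1 − ρ²) is 0.09/0.91 = 0.0989. Omitting baseline altogether would therefore cost 9.9% in variance, which is all that is at stake.

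**Results at ρ = 0.3**

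| SD of change | Weight on month 3 / month 18 | r | Retained | Variance ratio | Power |
|---|---|---|---|---|---|
| constant | 0.32 / 0.39 | 0.61 | 85% | 1.015 | 79.5% |
| time^0.25 | 0.78 / 0.19 | 0.36 | 59% | 1.040 | 78.6% |
| square root of time | 1.13 / 0.07 | 0.19 | 35% | 1.065 | 77.8% |
| proportional to time | 1.29 / 0.01 | 0.12 | 22% | 1.077 | 77.4% |

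Example, square root of time: 1 + 0.0989 × (1 − 0.19)² = 1.065.

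**Range over ρ.** At ρ = 0.2 the ratios run from 1.007 (constant SD) to 1.033 (SD proportional to time). At ρ = 0.4 they run from 1.025 to 1.146, the latter with power of about 75%. An exchangeable correlation of 0.8 combined with a growing SD gives larger losses.

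**Simulation check.** Fits with 20% exponential dropout at 12 months (300 trials per setting, 230 against 310 subjects assumed, ρ = 0.3, no true effect) gave mean estimates within 0.002 of zero. Squared ratios of the model standard errors were:
- constant SD: (0.0145/0.0144)² = 1.01;
- SD proportional to time: (0.0222/0.0214)² = 1.08;
- random-slope model: (0.0188/0.0183)² = 1.06.

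The ratios of the empirical variances were 1.02, 1.09 and 1.10.

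**Chance imbalance.** Under the null scenario in Table 9.2 of the simulation plan, control averages 179.1 subjects and the two 10 mg/kg arms 103.6 + 94.1 = 197.7. One standard error of baseline imbalance is √(1/179.1 + 1/197.7) = 0.10 baseline SD. The uncorrected part is ρ × SD₁₈ × (1 − r) × 0.10. SD₁₈ follows from 0.15 at 12 months:
- constant SD: 0.3 × 0.15 × 0.39 × 0.10 = 0.002;
- SD proportional to time: 0.3 × 0.225 × 0.88 × 0.10 = 0.006.

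The sign is random. This is the same lost precision seen in a single allocation, not an addition to the variance ratios.

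**The case against.** A common-slope MMRM is a legitimate model, and the SAP does not contradict itself here. Four objections carry weight.

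- **The inputs that decide the size are missing.** A reader might infer that the 18-month estimate loses most of its baseline adjustment. The documents do not support that as a flat statement. With constant SD about 85% is kept; most is lost only when the SD grows as the square root of time or faster. The linear profile in the simulation plan (12% at week 6, 100% at week 52) does not settle it, because it describes the treatment effect and not the baseline slope or the spread.
- **The visit set matters.** Adding the simulation plan's week-6 visit lowers the common slope to about 5% to 7% of the 18-month slope when the SD grows. The 3-monthly schedule in Section 8.1 gives about 12% to 19% at ρ = 0.3.
- **Amyloid PET is barely affected.** It is the only endpoint with SDs at two times (0.27 at 12 months and 0.4 at 18, Section 4). With scans at those two times, correlation 0.80 and ρ = 0.3, r is 0.61, about 85% is retained and the variance rises 1.5%.
- **The planned ANCOVA has its own slope.** Fitted at 18 months, it escapes the constraint.

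The first three limit the claim to a conditional one about the clinical scales. The fourth holds in part: the ANCOVA omits the strata and region and, fitted at 18 months, uses only subjects observed then.

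A reader might also infer bias from adaptive allocation or the APOE4 restriction. APOE4 status and clinical subgroup are already in the model, nothing in the SAP shows a remaining imbalance in baseline scores, and the simulation found no bias.

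**Conclusion.** The point stands as a modest efficiency improvement. It is neither an error in the plan nor a source of systematic bias. As written, the MMRM fits one baseline slope to all visits, and it governs the 18-month clinical comparisons. At an assumed ρ of 0.3 with AR(1) correlation 0.8, the 18-month residual variance is about 1.5% too high with constant SD and about 6% to 8% too high with SD growing as the square root of time or faster. That is about 0.5 to 3 points from 80% power. The SAP supplies neither the SD pattern nor the baseline correlation, so where the trial falls in this range cannot be determined from it. The Bayesian primary analysis does not use this model.

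**What to change.** In Sections 5.4.1.2, 5.4.4 and 5.8, add a baseline-by-visit interaction as a fixed effect to the MMRM for ADCOMS, CDR-SB, ADAS-Cog, MMSE and FAQ. Each visit then has its own baseline slope (r = 1 at month 18), and the full adjustment is restored whatever the SD pattern. With six visits this is five extra parameters, a few degrees of freedom out of several hundred subjects. No data collection changes.

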5.4.2 Adaptive Trial Definitions

Clinically Significant Difference (CSD): The CSD used in the adaptive model relative to the change from baseline over time for placebo in the derived ADCOMS. The CSD for this study represents an approximate 25% reduction compared to placebo in the progression of AD as measured by the derived ADCOMS.

Maximum Effective Dose (d_{Max}): The dose that achieves the greatest treatment effect.

ED₉₀: The ‘simplest’ dose regimen that achieves at least 90% of the d_{Max} treatment effect. The term ‘simplest’ reflects the preference for dosing frequency and amount when considering the treatment arms for the study and while taking efficacy into account (monthly administration is preferred over bi-weekly administration and lower doses are preferred over higher doses, with priority placed on frequency of administration). Thus, the rank order of prioritized doses (beginning with the simplest) is: 5 mg/kg Q4wk, 10 mg/kg Q4wk, 2.5 mg/kg Q2wk, 5 mg/kg Q2wk, and 10 mg/kg Q2wk.

Early Success: The study meets early success criteria if the probability that the ED₉₀ at 12 months of treatment is better than the placebo by the CSD is at least 0.95. Early success is achieved before all subjects complete 12 months of treatment and can only be determined once ≥ 350 subjects are randomized. If early success is declared prior to full randomization, the randomization of new subjects will stop. Subjects already randomized into the study will receive 18 months of treatment.

Futility: The study meets statistical futility criteria if the probability that the ED₉₀ is better than the placebo by the CSD is less than 0.05 (with ≤ 300 subjects randomized) or 0.075 (with ≥ 350 subjects randomized) at 12 months of treatment. If the study meets statistical futility criteria, the sponsor will make the final decision pertaining to study futility after reviewing recommendations by the DSMB. Based on Sponsor's final decision, if the study continues to randomize subjects, it will be considered a failed study.

Study Success: The study will be considered a success if either of the following criteria are met for the 12 month treatment endpoint:

1. The study meets early success criteria (as outlined above)
2. The study reaches complete randomization and the Bayesian analysis at completion of 12 months of treatment results in an ED₉₀ with at least an 80% probability of being better than the placebo by the CSD

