5.0 EVALUATION OF TRIAL SUCCESS AND FUTILITY

□

Interim analyses are planned beginning when 196 patients are enrolled and after approximately every additional 50 patients are enrolled (after 250, 300, 350, etc) as described in [Section 4.0](#). If the trial should continue to the maximum sample size of 800 patients, post accrual interim analyses are planned 3, 6, and 9 months after the 800th patient is enrolled. If the trial is not stopped early for futility, all enrolled patients will be followed for 18 months. The final evaluation of efficacy will occur when all enrolled patients have completed follow-up for the primary endpoint.

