Table 9.4 shows the probability of success by arm for each scenario. This is the probability each arm achieves at least a 95% probability of being better than control by the CSD during the trial, or if the trial should run to completion, at least an 80% probability of being better than control by the CSD. The true ED₉₀ for each scenario is shown in bold italics.

		5Q	10Q	3BM	5BM	10BM
1	Null	0.031	0.025	0.03	0.017	0.022
2	Small Effect	0.048	0.082	0.044	0.052	0.126
3	BM Good	0.06	0.165	0.048	0.112	0.415
4	Q Low	0.018	0.05	0.044	0.139	0.727
5	Both Good	0.048	0.17	0.041	0.1	0.627
6	U-Shape Good	0.14	0.192	0.205	0.316	0.12
7	U-Shape Low	0.095	0.15	0.158	0.316	0.098
8	Small Increases	0.208	0.219	0.17	0.136	0.193
9	One Works	0.02	0.017	0.018	0.011	0.626
10	All 0.04	0.19	0.172	0.171	0.104	0.11
11	All 0.06	0.277	0.219	0.207	0.124	0.135
12	All 0.08	0.285	0.232	0.217	0.139	0.122
13	Medium Effect	0.055	0.138	0.052	0.093	0.198

Table 9.5 show the probability each dose will have at least an 80% predictive probability of phase III trial success. The true ED₉₀ for each scenario is shown in bold italics.

		5Q	10Q	3BM	5BM	10BM
1	Null	0.011	0.007	0.009	0.005	0.005
2	Small Effect	0.022	0.058	0.017	0.037	0.101
3	BM Good	0.027	0.157	0.024	0.094	0.435
4	Q Low	0.001	0.008	0.009	0.078	0.888
5	Both Good	0.011	0.113	0.006	0.057	0.800
6	U-Shape Good	0.126	0.194	0.194	0.375	0.071
7	U-Shape Low	0.075	0.138	0.141	0.348	0.059
8	Small Increases	0.222	0.247	0.146	0.12	0.161
9	One Works	0.003	0.003	0.003	0.003	0.641
10	All 0.04	0.196	0.16	0.151	0.084	0.078
11	All 0.06	0.325	0.219	0.207	0.098	0.095
12	All 0.08	0.375	0.241	0.199	0.096	0.084
13	Medium Effect	0.028	0.12	0.025	0.073	0.182

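### After early success the main text ranks the complete 12-month analysis below the interim snapshot, while Appendix 13.2 calls it the final one; the source of the reported dose and effect must be settled

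*SAP*

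**What the plan says.** **Main text.** Section 5.4.1.2 runs the conventional ED90-versus-placebo comparison twice after early success, on the data before the interim analysis and again at 12 months, and ranks them: "the analysis at the end of 12 months assessment will be considered as sensitivity analysis to the analysis at early success". Section 5.4.1.1, headed Sensitivity Analyses, does the same for the Bayesian result: "the primary analysis as well as the above sensitivity analysis will be repeated after all subjects have either completed 12 months follow-up". Subjects who drop out before then count as finished for this purpose. Section 5.4.2 defines early success as a probability that the ED90 is "better than the placebo by the CSD is at least 0.95", and gives two routes to success: "The study will be considered a success if either of the following criteria are met for the 12 month treatment endpoint". The first route is early success by itself. No rule covers complete data that disagree with the snapshot or name a different ED90.

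**Appendix 13.2.** Section 5.0 states: "The final evaluation of efficacy will occur when all enrolled patients have completed follow-up for the primary endpoint". The worked example in Section 7.0 stops for early success at 700 subjects and then presents a final analysis after all enrolled patients have completed follow-up. Sections 5.4 and 5.5 judge phase III promise and superiority to control at the conclusion of the study.

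**The concern.** This is a dose-finding trial, so its main products are a named dose and an effect size. After an early stop, the main text makes the interim look the lead source for both. That look is chosen because its probability crossed 0.95, so its estimate tends to be too favourable. It may also rest mainly on 52-week values imputed from earlier visits. Section 5.4.2 keeps subjects already randomised on treatment for 18 months, so the complete 12-month data will exist, yet they are given the lower rank.

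The report could therefore lead with an ED90 and an effect that the trial's own complete data do not support. Two parts of the SAP would also give different answers about which analysis is final.

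**Working it through.** All inputs are from Appendix 13.2 (Sections 2.2, 3.4, 5.2 to 5.4, 7.0, 8.2 and 9.0; tables at 40% dropout) unless marked as assumed.

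**1. Reproducing the SAP's figure.** Summing success by arm (Table 9.4) under the null: 0.031 + 0.025 + 0.030 + 0.017 + 0.022 = 0.125, the Type I error in Table 9.1. All 13 scenarios agree within 0.001, so each successful trial credits one arm.

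**2. How complete the snapshot is.** In the worked example:
- Subjects with 52-week data at the 700-subject look: 38 + 20 + 18 + 15 + 18 + 19 = 128 of 700 (18%). In the declared arm (10 mg/kg biweekly) it is 19 of 160.
- At the end: 114 + 44 + 53 + 74 + 42 + 93 = 420 of 700 (60%).
- Model-estimated difference from control for the declared arm: 0.074 − 0.006 = 0.068 at the look, and 0.067 − 0.012 = 0.055 at the end.
- Its probability of beating control by the CSD: 0.957, then 0.923.

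**3. Change of named dose.** If Tables 9.3 and 9.4 were taken at the same time, no arm could be credited with success more often than it is identified as the ED90. A lower bound on trials that name one dose at success and another in Table 9.3 is the sum over arms of max(0, Table 9.4 − Table 9.3).
- Q Low: (0.018 − 0.001) + (0.050 − 0.009) + (0.044 − 0.010) + (0.139 − 0.082) = 0.149
- Both Good: (0.048 − 0.012) + (0.170 − 0.117) + (0.041 − 0.006) + (0.100 − 0.060) = 0.164

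| Scenario | Table 9.1 success | Sum of Table 9.4 | Lower bound on change |
|---|---|---|---|
| Both Good | 0.987 | 0.986 | 0.164 |
| Q Low | 0.978 | 0.978 | 0.149 |
| All 0.08 | 0.994 | 0.995 | 0.098 |
| U-Shape Good | 0.972 | 0.973 | 0.057 |
| All 0.06 | 0.961 | 0.962 | 0.055 |

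Four other scenarios give 0.016 to 0.024. The remaining four give zero. In Q Low the true ED90 is credited at success in 72.7% of trials and identified in Table 9.3 in 89.8%. In Both Good the figures are 62.7% and 80.5%.

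The SAP does not say when Table 9.3 is taken. The end-of-study reading is inferred, with support from Table 9.5: its criterion applies at the conclusion of the study, and it does not exceed Table 9.3 in any of the 65 cells.

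**4. Null trials.** Table 9.1 gives early success 0.119 of the total 0.125. Table 9.5 sums to 0.011 + 0.007 + 0.009 + 0.005 + 0.005 = 0.037.

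To see how the phase III bar relates to the CSD rules, I used

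PP = Φ((est/se₃ − 1.96) / √(1 + s²/se₃²)), with se₃ = 0.15 × √(2/250) = 0.0134.

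The posterior SD s is not tabulated. The example implies (0.068 − 0.03)/Φ⁻¹(0.957) = 0.022 at the look and (0.055 − 0.03)/Φ⁻¹(0.923) = 0.0175 at the end.
- At the early boundary, est = 0.03 + 1.645s. For assumed s from 0.006 to 0.04, PP is 0.82 to 0.95, so an early success meets the phase III bar when it is declared.
- At the 80% CSD boundary, est = 0.03 + 0.8416s. For assumed s from 0.014 to 0.03, PP is 0.79 to 0.81, so the phase III bar is close to the 80% CSD rule.

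Hence at least 0.119 − 0.037 = 0.082 of null trials (0.082/0.119 = 69% of null early successes) miss the phase III bar later. The same bound for Small Effect is 0.281 − 0.235 = 0.046, or 16% of its early successes. The other 11 scenarios give no positive bound.

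**The case against.** **The appendix does not contradict the success rule.** A reader might infer that it does. In fact Section 5.2 stops for early success, Section 5.3 tests completion success only if the trial was not stopped early, and Section 9.0 counts success by either route. The disclosed 12.5% Type I error already contains the 11.9% early successes. This objection stands: the conflict is only over which analysis is final for dose and effect.

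**The complete-data results are already planned.** Sections 5.4.1.1 and 5.4.1.2 repeat both analyses, and Section 5.4.4 takes the ED90 for its key secondary comparisons from the 18-month Bayesian analysis. A discrepancy would be visible. This stands too, but visibility does not settle which 12-month result leads.

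**The tables show less than they might seem to.** Lost successes are shown only for Null and Small Effect, through a proxy. The dose-change bound needs the inferred timing of Table 9.3. In All 0.08 every arm has the same effect, so a change of name costs nothing there. The worked example keeps both its dose and its success. Heavy imputation is not general either, since looks 6 and 9 months after accrual have more 52-week data. All of this limits the size of the point. It does not touch Q Low and Both Good, where the best arm is set at 0.10 and every other arm at 0.06 or less (Table 8.2).

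**The branch appears closed.** Section 3.2 ties the extension to early success at an interim or the 12-month Bayesian analysis, and Section 3 says its conditions were not met. The opening list shows interim reports up to 800 subjects and 12 months after accrual. This lowers the urgency.

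**Conclusion.** The point holds as an inconsistency and a poor choice of lead analysis after early success. Sections 5.4.1.1 and 5.4.1.2 put the snapshot first, and Appendix 13.2 (5.0 and 7.0) puts full follow-up first. On the end-of-study reading of Table 9.3, the named dose changes in at least 14.9% of Q Low and 16.4% of Both Good trials. Under the null, 11.9% of trials stop for success, but only 3.7% have a dose meeting the phase III bar. That comparison assumes the approximate predictive-probability formula and the stated range of s.

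Two stronger readings are not supported. The first is that many successes reverse in general: in clearly effective scenarios the demonstrated problem is the dose named, not the loss of success. The second is that success after an early stop should also require 80% at full follow-up. That would redefine success. By the Table 9.5 proxy it would lower BM Good from 0.801 to 0.737, U-Shape Low from 0.817 to 0.761, Medium Effect from 0.537 to 0.428 and Small Effect from 0.353 to 0.235, so two scenarios would fall below 80%.

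Severity is moderate to low. The rule remains in v4.0 but probably had no effect on this trial's result.

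**What to change.** In Sections 5.4.1.1, 5.4.1.2 and 5.4.2, state that:

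- early success stops randomisation, and the success rule and its disclosed Type I error stay as they are;
- the reported ED90, its posterior probabilities and its effect estimate come from the Bayesian analysis performed when all randomised subjects have completed or left 12-month follow-up;
- the main ED90-versus-placebo MMRM uses the same complete data and the ED90 identified from them;
- the interim snapshot is reported beside these as supportive, and any difference in named dose or effect is described.

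Align the wording with Appendix 13.2, Section 5.0, and state in Section 9.0 when Tables 9.3 and 9.4 are taken. The cost is SAP text only. It needs no extra subjects, visits or analyses, because both sets of results are already planned, and the operating characteristics for success do not change.
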